### 7.3.3 Data Analysis

For each model, a contingency table will be devised so summary accuracy statistics including sensitivity, specificity, Positive Predictive Value (PPV) and Negative Predictive Value (NPV) can be calculated. In addition, a calibration plot will show the agreement between observed and expected results, with a LOESS smoother and confidence intervals being used. Discrimination will be

calculated with the C-statistic, plotting on a Receiver Operating Characteristic (ROC) curve, or by further examination of the calibration plot. These results will all be unadjusted at the derivation stage and the analysis will only show the apparent performance of each model.

## 7.4 Secondary outcome analysis

### 7.4.1 Sample size for cohort 2

This will be the maximum number of non-conveyed patients that can be attained in the same data collection period as cohort 1. A YAS report has established there were 93,271 non-conveyed patients between July and December 2018. With a 5% demand increase for 1 year forecasting, and assuming there will be no change in the percentage of non-conveyed, the sample size estimation would be 97,935.

### 7.4.2 Data preparation and missing data for cohort 2

This is the unlinked ambulance service data and only includes patients that were not conveyed to hospital. Its purpose is to sense check the derived models performance in a sample of low-mid acuity patients. All variables will be explored with a frequency analyses undertaken to identify missing data. The same preparation and methods for dealing with missing data will take place in the ambulance clinical variables as cohort 1 (see protocol section 10.3.1). No outcome will be generated as it is unlinked.

### 7.4.3 Internal validation

For the logistic regression model this can be performed using bootstrapping of cohort 1 to measure the optimism and then apply the shrinkage factor to the beta coefficients. For methods such as random forest modelling, they would need alternative methods such as cross-validation. Once all models have been internally validated, they will be applied to cohort 2.

There will be a sub-group analysis using non-random splitting of cohort 1 according to individual variables. The performance in the sub-groups can then be plotted in a graphical way such as a calibration plot or ROC curve. This will enable the identification of groups of patients the model is more vulnerable/ robust towards.

### 7.4.4 Model selection

Once all adjusted models have been created and tested on cohort 2, there will be a comparative analysis of model performance using the same methods described above. The CI will then present the models to a small expert panel for independent confirmation. This panel will be a combination of clinicians and statisticians.

## 8 Data Management

### 8.1 Data collection tools and source document identification

Yorkshire Ambulance Service has an ePCR system in place across the whole region. This is a compulsory system for paramedics to create and complete individual care records for each patient which begins at arrival on scene, and is completed once the patient is handed over. This document forms the source document for each patient that will be eligible in this project. The sample size in section 10.2 is in effect calculating the number of source documentation required for model derivation and validation.

Within each source document is the variables required to derive and validate the model. An example of the variables within can be seen in table 1 (above). The variables are mainly categorical and presented as drop down lists. The other type of variable captured is continuous such as age. The clinician is expected to fully complete each record however not all fields are compulsory capture.

This is a retrospective study and as such, there will be no attempt to maximise completeness of data. The sample size has been inflated to account for expected source document attrition at the point of data retrieval. The methodology has accounted for the handling of missing data.

## **8.2 Data handling and record keeping**

### **8.2.1 Data linkage**

This study is using routine ambulance service data and linking each episode to the matched ED record to create the final dataset. The initial data retrieval will be done by the data controllers of the ambulance service data. A final data specification will be submitted to ensure only the required data is retrieved. On retrieval, a unique ID will be created for each ePCR and entered as a new variable. Once this has happened, the data will be split into a clinical extract (which is anonymised) and an identifiable extract. The unique ID will be present in both extracts.

The clinical extract will be transferred securely to the CI, and the identifiable extract will be transferred to NHSD for data linkage. A Data Sharing Agreement (DSA) will be created between NHSD and Yorkshire Ambulance Service for the transfer of data.

NHSD will then link the ambulance service record to the associated ED record. This will be done using hierarchical matching of key variables. Once maximum data linkage has taken place, NHSD will delete all identifiable data from the dataset, leaving only the unique ID. This anonymised dataset will be transferred securely to the CI. Once the CI has both datasets, they can merge them using the unique ID. Please see the study flow chart above.

### **8.2.2 Data management**

Once the data has been linked, anonymised, and sent securely to the CI, the data will be stored securely at the UOS. This will be in concordance with the Information Governance policies and procedures.

The storage of the dataset will be held and accessed only by the CI and their supervisory team, ensuring confidentiality and integrity of the data. All computers used to host servers are kept in secure premises where access is restricted to authorised individuals. No data is or will be stored on laptop computers. There is a strict policy of not accessing data on the network from laptop computers whilst in insecure, public locations.

The dataset will be stored on a Virtual Machine (VM) which is secured and maintained by The UOS Corporate Information and Computing Services (CiCS). CiCS administrators have policies in place which address network security (especially threats from outside the campus network) and software maintenance. The VM is privately addressed; it is not accessible from outside the campus network. Access to the VM (only possible from within the campus network and from specified IP addresses) is granted only to a limited number of user accounts, all of which require authentication by username and password. The machine-level firewall policies permit incoming traffic only from specified IP addresses.

### **8.2.3 Access to data**

Only the CI and the direct supervisory team will have access to the data within the UOS.

### **8.2.4 Archiving**

Storage of the dataset and associated folders are in folders designated with a 'time to live', projected to be a period of 10 years. After the 10 year period has expired, the research database will be removed from the study-specific system folder and archived in a secure UOS networked storage area, accessible only to administrators of the storage network.

## 9 Monitoring, Audit & Inspection

This study may be audited as part of the routine audit process as laid out in the sponsors research governance policy. All source documents and essential documents will be available to the sponsor for audit for at least 10 years.

## 10 Ethical And Regulatory Considerations

### 10.1 Research Ethics Committee (REC) review& reports

Ethical approval will be sought from the Health Research Authority (HRA) including support from the Confidentiality Advisory Group (CAG). This is for obtaining identifiable patient data without consent. All amendments will be submitted to the HRA for approval prior to implementation. All correspondence with the HRA will be recorded and stored in the local study folder, which can be accessed by the sponsors. An annual progress report will be submitted to the HRA within 30 days of the anniversary date on which the favourable opinion was given, and annually until the study is declared ended. It is the CI's responsibility to produce the annual report and also to notify the HRA of the end of the study.

### 10.2 Peer review

This study has had a high quality peer review by the funder, as well as the sponsor.

### 10.3 Public and Patient Involvement

This project has been heavily influenced by the public. The Sheffield Emergency Care Forum is a Public Involvement and Engagement forum that is situated at the UOS. For the 12 months leading up to funding submission, this project has had a standing agenda at their quarterly meetings. Through an iterative process, they have steered the design of the project.

A small grant from the Research Design Service (RDS) was won to conduct three Public Involvement events. There were a total of twenty two public members involved who captured diversity in socio-economic status, gender, age, disability and ethnicity.

The members of the public who helped in the design of the research have been invited to a Whatsapp group. This is a digital messaging application that is secure with end-to-end encryption. Those who have access to the application but never used it will be helped. Those who don't have access but would like to participate will be invited to face to face meetings and caught up on a one-to-one basis. The purpose of the Whatsapp group is to have a longitudinal conversation with the public about the project. It is understood that the PhD is a learning experience and highly likely to change as the project progresses. As these changes are being made, the public will be asked in advance of their thoughts. They will also be invited to comment on reports to ensure the language can be understood by everyone. There will be annual meetings with members of the group to consolidate conversations in the Whatsapp group, and also to present and discuss the progress of the project. In the first phase of the research the panel will be invited to help produce a lay summary of the risk prediction model. This phase could be considered esoteric and complicated and the public will be invaluable in ensuring the summary is clear and concise.

In the second phase, there will be an opportunity to present progress with the study, overview the tool and how it works. This will also provide an opportunity for discussion and views to be shared about the tool. The output from this consultation will be used to influence the ongoing development and implementation of the tool. Willing volunteers will be asked to create a video for the public introducing the tool and its purpose. They will also be invited to co-author relevant publications, and abstracts will be submitted to INVOLVE and other conferences, offering them an opportunity to present.

The public's acceptability of using patient identifiable data in this study without consent has been tested on three separate occasions with three different public involvement groups. The SEFC held a discussion about the project on the 10/08/2018 and there was a consensus of support from the group about using identifiable data

in this study without consent. On the 13/08/2018 a random group of public members were identified using an NIHR Public Involvement grant. They felt the method of using identifiable data without consent was justified and supported the methodology. On the 16/08/2018 the Sheffield Addiction Recovery Research Panel (SHARRP) were consulted and felt the research question was important and that the methodology was appropriate as large numbers were required to create a model.

#### **10.4 Protocol compliance**

Any breach of protocol will be reported via the YAS Datix system to notify the Research and Development department at YAS. Duty of Candour will be considered in consultation with the YAS Duty of Candour specialist. Furthermore, the UOS Information Governance Committee will be informed and will undertake a further investigation of the breach.

#### **10.5 Data protection and patient confidentiality**

This protocol complies with each principle of the Data Protection Act 2018. Below is a summary statement for each principle.

##### **10.5.1 Fair Processing**

The legal basis for collecting and processing of patient identifiable data is that it is a task in the public interest.

The data is being used for linking and validating data from different healthcare providers in order to derive and validate a risk prediction model to support decision-making.

Sensitive patient data is being processed under the condition that the data is processed for medical purposes by individuals subject to an equivalent duty of confidentiality as exercised by a health professional.

The data processing is being used only for this legitimate reason and the use of data to link healthcare provider records will not have any adverse effects on individuals whose data is linked.

This data is being collected without the consent of patients, however this is justified on the grounds consistent with Article 4 of the Data Protection (Processing of Sensitive Personal Data) Order 2000, which states that processing data without consent may be justified when in substantial public interest and is necessary in a case where the data controller cannot reasonably be expected to obtain the explicit consent of the data subject.

##### **10.5.2 Used for specified purposes**

(Not required)

##### **10.5.3 Minimum necessary for the purpose**

There will be the minimum amount of data collected which will satisfy the required sample size for the study. Only variables that will have potential to act as a candidate predictor, or are necessary for data linkage will be requested.

There will be the linkage of data from YAS, and data held by NHSD. Only data items of name, address including postcode, date of birth, age, gender, NHS number and incident/episode number are required for data linkage. A more limited number of fields are not possible to specify or collect as the nature of YAS data is such that for different cases different personal identifiers will be missing i.e. for some YAS cases, no home address will be specified as the incident may have happened away from the individuals' home. In this case age, gender and name/ NHS number will be required to enable linkage.

#### **10.5.4 Accuracy**

It will be ensured that all information collected and stored from the service providers is recorded accurately and reflects the source data. There will be a dependence on the accuracy and completeness of data collected by service providers at time of episode. There will only be data retrieval for linkage of specific episodes which have occurred on a specific date and there will not be any follow up or contacting of patients at a subsequent date. Thus there will be no contemporaneous need to ensure records are kept up to date.

#### **10.5.5 Kept for minimum time necessary**

As soon as the data is linked, all identifiable data will be destroyed by NHSD.

#### **10.5.6 In accordance with the rights of data subject**

This study is requesting permission to access data without consent of patients. The study design has been carefully considered to protect the personal and identifiable information of service users. As such, none of the research team will receive this sensitive information.

There will be no direct marketing undertaken, this data is being processed for the defined process of data linkage to form a large dataset containing de-identified data, which is being used to develop a predictive model.

Regarding holding inaccurate data – it is possible that data will become out of date as the study is undertaking retrospective data analysis. Therefore inevitably some patients will move address or have other changed circumstances. However the research team will ensure that the data recorded and processed is accurate at the time i.e that it accurately reflects the data provided by the healthcare providers.

#### **10.5.7 Security and confidentiality protection**

Both YAS and NHSD have robust systems in place for the storage, retrieval and processing of patient identifiable information. In addition, they hold the knowledge and expertise to ensure the security of sensitive data. Identifiable data will only be seen by the BI department in YAS who will separate the context (clinical information) from the identifiable data. This protects patient confidentiality. It also ensures NHSD only process the minimum amount of variables for data linkage. As soon as NHSD have linked the data, the identifiers will be destroyed. This anonymised dataset can then be securely transferred to the UOS.

The CI and their supervisors are employees or part of The UOS and are subject to The UOS Information Security Policies. This includes complying with the Data Protection Act 2018 and UOS Information Governance Policy which requires renewal every 2-years. The CI and the sponsors are bound by the Information Governance policies and procedures of Yorkshire Ambulance Service and are regularly re-certified on these.

Physical security is maintained by University staff working in secure locked offices in alarm coded corridors. Staff members trained to log off from their computers whenever they are away from their desks

#### **10.5.8 Not disclosed outside of the EU**

No patient or sensitive data on individuals will be disclosed outside the EU.

## **10.6 Financial and other competing interests**

No competing interests

## 10.7 Amendments

Any amendments to the protocol will be submitted to the HRA for categorisation and consideration as appropriate.

## 10.8 Access to the final study dataset

During the study, only the student investigator, the CI and immediate supervisory team will have access to the final study dataset at the UOS. On completion of the study, the Yorkshire Ambulance Service will be responsible for formalising archive arrangements.

# 11 Dissemination Policy

## 11.1 Research outputs

### 11.1.1 Anticipated research products

- A toolkit that can support clinicians in deciding the likelihood of an avoidable attendance before transporting the patient. This can be built into an electronic patient care record and used to support clinical assessment and decision making. Outputs will be disseminated through peer review publications, presentation at relevant conferences.
- A Systematic review of risk prediction modelling in the urgent and emergency care system.
- New knowledge on what clinical assessment variables contribute most to risk stratifying patient's on scene.
- New knowledge on using risk prediction modelling in the prehospital setting and the potential feasibility of more complicated models such as machine learning in assisting clinical decision making.
- New knowledge on how to manage patient expectations on-scene.
- New knowledge on how to influence/change a clinician's decision on-scene by presenting them with patient risk.
- Two anonymous linked datasets of clinical care prehospital and in hospital data that other projects can use for further analysis.
- Further research plans for refining the tool, implementation and testing under real world conditions such as a randomised controlled trial.

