## *The case-mix problem*

The majority of ambulance service patients require less critical interventions and more community based care. In response to this, policy has been driving paramedics to make autonomous and dynamic decisions about their patient care before transporting them to the ED. This theme was particularly emphasised in the Urgent and Emergency Care Review Team (UECRT) report in 2013. One of the main outcomes they aimed to achieve in the report were for those with an urgent need to access healthcare be provided with a highly responsive, effective, and personalised service outside of hospital.

Interventions have been developed to stratify patient risk on-scene and decide where the best care of a patient should be. One example that has been adopted by numerous ambulance services is the paramedic pathfinder tool. The tool was user tested in 2014 when a sample of 481 patients had the tool applied to them with results showing sensitivity of 94.83% and specificity of 57.9%. The tool was highly risk averse with almost half of the patients being transported to the ED, when the care could have safely been elsewhere. Furthermore, O Hara et al. used qualitative methods to conclude that paramedic decision making is multifactorial and complicated. They emphasised a decision not to transport a patient was the most challenging.

More evidence is required to risk stratify patients and allow paramedics to make more discriminate ED transport decisions on-scene.

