# 2 Rationale

This research is supporting paramedics to make more appropriate and effective decisions for patients who may not require the level of care provided by a hospital. It is important as it is aiming to navigate care decisions that will safely provide patients with the right care, first time. If a paramedic can see the likelihood that their patient may have an avoidable attendance, it opens up an opportunity to explore community options. It also empowers the patient to be an active partner in developing a self-care plan. The whole urgent and emergency care system would benefit from this research. If paramedics can make safe non-transport decisions it frees their capacity to assess a patient still waiting for help. With less patients being transported to the ED with low acuity problems, it will minimise delays in caring for those who do need specialist ED interventions. For community care it will identify patients that require out of hospital services so that they can get the right level of care promptly. This project does recognise when a paramedic assesses a patient, there are six possible outcomes relating to a transport decision. Firmer evidence surrounding outcome measures for the other five dispositions is needed before tools that can accurately signpost patients to any service can be developed.

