## 6 Participant Eligibility Criteria

### 6.1 Inclusion criteria

Inclusion 1  
(for Cohort 1 ED  
information)

- Age 18 years old or older.
- Transported to ED by Yorkshire Ambulance Service between July 1st 2019 and December 31st 2019.
- Have an ED Care record of the event.

Inclusion 2  
(for Cohort 1  
Ambulance  
information)

- Age 18 years or older.
- Assessed by a qualified ambulance clinician ((either paramedic (of any level) or technician grade II)).
- Had an electronic patient care record completed.
- Transported to an ED between July 1st 2019 and December 31st 2019.
- Were handed over and booked in as a patient to the ED

Inclusion 3  
(for Cohort2)

- Age 18 years or older.
- Assessed by a qualified ambulance clinician (either paramedic or technician grade II).
- Had an electronic patient care record completed.
- Discharged on scene and not transported between July 1st 2019 and December 31st 2019.

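### The model is derived only in conveyed patients but offered for the transport decision itself; its calibration in patients now left on scene is unknown and cannot be tested in this study

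*Protocol*

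**What the plan says.** **Intended use.** Protocol section 11.1.1 lists as its first product "A toolkit that can support clinicians in deciding the likelihood of an avoidable attendance before transporting the patient". The background (The case-mix problem) states the need as "More evidence is required to risk stratify patients and allow paramedics to make more discriminate ED transport decisions on-scene". The rationale in section 2 adds "If a paramedic can see the likelihood that their patient may have an avoidable attendance, it opens up an opportunity to explore community options". The study title, and section 11.2.1 on dissemination to the public, both describe support for the decision whether to transport at all.

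**Derivation population.** Under section 6.1, the ED side of cohort 1 is limited to patients "Transported to ED by Yorkshire Ambulance Service between July 1" and the end of December 2019 who have an ED record. On the ambulance side they must also satisfy "Were handed over and booked in as a patient to the ED".

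**Patients left on scene.** Cohort 2 consists of patients "Discharged on scene and not transported between July 1" and the end of December 2019. On this cohort, section 7.4.2 says "Its purpose is to sense check the derived models performance in a sample of low-mid acuity patients" and also "No outcome will be generated as it is unlinked". Sections 3.2 and 3.2.1 nevertheless make simulated transportability to non-conveyed patients a secondary question. Section 7.4.4 treats the models as having been tested on cohort 2 before their performance is compared.

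**The concern.** Everyone used to fit the model has passed through the decision that the model is meant to inform. What is estimated is the probability of an avoidable attendance given the recorded variables **and** conveyance. What a crew would read from the tool before deciding is the probability given the recorded variables alone. The two agree only if, at fixed recorded variables, the crew's choice carries no further information about avoidability.

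No planned step examines this:

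- The bias assessment in sections 4, 7.1 and 7.3.1 compares linked with unlinked records. Both sets were drawn under the cohort 1 criteria, so both are conveyed patients.
- Bootstrapping, cross-validation and the subgroup splits in section 7.4.3 all stay within cohort 1, so every resample carries the same restriction.
- Cohort 2 has predictions but no outcomes, so calibration, discrimination and misclassification cannot be calculated there.

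At stake is what the study may conclude. A model that looks well calibrated in cohort 1 could be presented as valid for every patient assessed on scene, without evidence for those crews now discharge.

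**Working it through.** **1. The plan's own figures.**

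- Cohort 1 (section 7.2): 520 × 50 / 0.09 = 288,889; × (1 + 0.20 + 0.077) = 368,911. Reproduced.
- Cohort 2 (section 7.4.1): 93,271 × 1.05 = 97,935. Reproduced.
- Total (Study Summary): 368,911 + 97,935 = 466,846. Reproduced.

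**2. Share of assessed patients outside the derivation population.**

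- 2018 counts (section 7.2): 735,053 / 919,635 = 79.9% conveyed, so 20.1% were not. The section prints 74.9% conveyed beside these counts, which would leave 25.1%.
- Planned cohorts: 97,935 / 466,846 = 21.0%.
- Local rate cited in section 2 (Non-conveyance): 30.6%.

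The range is about 20% to 31%.

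**3. Does conditioning on conveyance bias the prediction?** The protocol gives no avoidable rate for patients left on scene, so this can only be illustrated. From the documents come the avoidable rate among the conveyed (9%, section 7.2; up to 16.9%, section 1) and the planned share left on scene (21%). Every coefficient is an assumption.

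Set-up: 1,000,000 patients, one recorded predictor x and one unrecorded factor u, independent standard normals.

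- logit P(left on scene) = a + x + g·u
- logit P(avoidable) = b + x + h·u
- a is set to leave 21% on scene, and b to give 9% or 16.9% avoidable among the conveyed.
- A logistic model on x and x² is fitted in the conveyed only and applied to those left on scene.

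Predicted versus true avoidable percentage in patients left on scene, with O/E = true / predicted:

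| Selection | 9% among conveyed | O/E | 16.9% among conveyed | O/E |
|---|---|---|---|---|
| recorded x only (g = 0, h = 1) | 16.6 vs 16.5 | 0.99 | 28.3 vs 28.2 | 1.00 |
| u favours both, weak (g = h = 0.5) | 16.6 vs 19.7 | 1.19 | 28.7 vs 32.8 | 1.14 |
| u favours both (g = h = 1) | 14.8 vs 25.6 | 1.73 | 25.7 vs 40.4 | 1.57 |
| u opposite, weak (g = −0.5, h = 0.5) | 17.3 vs 14.6 | 0.84 | 29.4 vs 25.5 | 0.87 |
| u opposite (g = −1, h = 1) | 16.4 vs 9.1 | 0.55 | 28.0 vs 16.9 | 0.60 |

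The first row matters most. The two groups differ in average avoidability, yet the predictions are unbiased. A different case mix is not enough to cause bias; unrecorded selection is needed.

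**4. A wider range of effects.** In a second set-up the crew leaves the top 20.1% of x + b·u + logistic noise, and the outcome logit has slope 1.2 on x and an effect of u of size 0.5 to 1.5. At 9%, O/E in the non-conveyed is about 1.2 to 2.5 when u acts in the same direction on both, 1.0 with no unrecorded factor, and 0.85 down to about 0.3 when it acts in opposite directions.

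**5. Could recorded variables reveal it?** In the second set-up with same-sign effect 1.5 and true O/E about 2.47, calibration in the fifth of cohort 1 most like cohort 2 is 0.99, and about 0.01% of cohort 2 lies outside the range of cohort 1. Both checks look clean. With a single recorded predictor the range check is a simple one; with many predictors it would say more about case mix, but still nothing about u.

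**The case against.** The strongest reply is that cohort 1 is the right population for the need stated in section 1, which is to find likely avoidable conveyances while the patient is still with the crew. For a patient the crew would otherwise convey, fitting in the conveyed is correct. That stands, and it is why the remedy is to state this scope rather than redesign the study. It does not settle the matter, because the title, section 11.1.1 and section 11.2.1 are worded more broadly and nothing restricts use to that group.

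The protocol also does not ignore non-conveyed patients. Transportability is a secondary question, cohort 2 is applied to it, and section 11.1.1 foresees further testing such as a randomised trial. But without an outcome, cohort 2 can show only the distribution of predictions.

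A reader might go further and infer that predictions **will be too low** for patients now left on scene, so that the tool would push them towards transport. The documents do not support this. They give no avoidable rate for that group, do not say that crews act on unrecorded information related to avoidability, and fix no threshold or action rule. About 23 candidate variables, counted as 520 parameters, are to be used, among them working impression, NEWS, mental capacity and mobility, so much of the crew's reasoning may be recorded. The largest ratios also need an unrecorded factor (1.5) stronger than the recorded one (1.2). Under-prediction is plausible, since the protocol itself describes the decision as multifactorial and not all record fields are compulsory, but it remains an assumption.

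**Conclusion.** The point holds as a mismatch between claimed use and derivation population. Predictions are conditional on conveyance, and calibration in the 20% to 31% of assessed patients left on scene is unknown and cannot be tested with the planned data. This follows from sections 6.1, 7.4.2 and 11.1.1 and needs no modelling assumption.

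The size and sign of any miscalibration are not established. The range of about 0.3 to 2.5 at 9% avoidable is illustrative: it rests on assumed coefficients and a single unrecorded factor, and includes no bias at all. Its use is to show that the answer turns on something these data cannot reveal, so an unrestricted claim for use before the decision is unsupported in either direction.

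**What to change.** - In sections 3.1.1, 4 and 11.1.1, define the prediction as the probability of an avoidable attendance in a patient the crew would otherwise convey, and limit the claimed use to that group.
- In sections 7.4.2 to 7.4.4, describe the cohort 2 application as a display of predictions under a different case mix, not as a test of performance, and base the model comparison on cohort 1.
- Optionally, fit a membership model (conveyed versus discharged on scene) on the recorded ambulance variables of both cohorts, and report it as a description of overlap. State that it cannot detect unrecorded selection, and accompany it with a sensitivity range over assumed unrecorded selection of both signs.

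The first two items are wording only. The optional item is one regression and a short sensitivity analysis on data already requested. The downside is a narrower claim for the tool.
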